**STATEMENT OF COMPLIANCE**

This study will be conducted in compliance with the protocol, International Council for Harmonisation (ICH) E6 (R2) guideline for Good Clinical Practice (GCP), and the applicable regulatory requirements from the United States Code of Federal Regulations (CFR), including 45 CFR 46 (Human Subjects Protection); 21 CFR 50 (Informed Consent), 21 CFR Part 54 (Financial Disclosure), and 21 CFR 56 (Institutional Review Board [IRB]); as well as international regulatory requirements, if applicable.

All individuals who are responsible for the conduct, management, or oversight of this study have completed Human Subjects Protection and ICH GCP Training.

**LIST OF ABBREVIATIONS**

CARE	Cultivating Awareness and Resilience in Education
CDC	Centers for Disease Control and Prevention
CFR	Code of Federal Regulations
CI	Confidence Interval
CoC	Certificate of Confidentiality
COVID-19	Coronavirus Disease 2019
DCRI	Duke Clinical Research Institute
DUHS	Duke University Health Systems
GCP	Good Clinical Practice
HIPAA	Health Insurance Portability and Accountability Act
ICH	International Council for Harmonisation
IRB	Institutional Review Board
NIH	National Institutes of Health
NICHD	National Institute of Child Health and Human Development
PI	Principal Investigator
PP	Per-protocol
U.S.	United States

[figure not shown]
**PROTOCOL HISTORY OF CHANGES**

Version	Date	Summary of Changes
1.0	29 Sep 2022	N/A Original protocol

## PROTOCOL SYNOPSIS

Protocol Title:	ABC Mental Health: A behavioral study of K-12 teachers and school staff
NCT #	Pending
Phase:	N/A, a behavioral intervention
Study Intervention:	Behavioral
Objectives:	
Primary: Evaluate the impact of a teacher resilience program on mental health and well-being outcomes of K-12 teachers and staff
 
Exploratory: Examine teacher and staff classroom instruction and behavior management

Study Design:	Prospective, multi-site
Study Population:	Kindergarten through 12 th grade (K-12) school employees
Inclusion / Exclusion Criteria:	
Inclusion Criteria:
 
 
- Adult participant, defined as an adult (18 years or older) employed by a school working with youth in kindergarten through 12th grade.
 
- Fluent in the English language
 
 
Exclusion Criteria: N/A

Number of Participants:	Up to 1,000
Number of Sites:	Single coordinating site, direct-to-participant
Duration of Participation:	School employees will participate in the intervention up to 1 year; the study will last up to 2 years.

## 2 BACKGROUND INFORMATION AND RATIONALE

### 2.1 Background Information

#### 2.1.1 Background of Child Mental Health During COVID-19

As of December 2020, the severe acute respiratory virus coronavirus 2 (SARS-CoV-2) has caused over 74 million confirmed cases of Coronavirus Disease 2019 (COVID-19) and over 1.6 million deaths globally. Initially, children were thought to be minimally affected by this disease, representing < 2% of confirmed cases. However, more recent studies describe increased incidence of multisystem dysfunction and some association to prior or concurrent SARS-CoV-2 infections in children. Thus, spread of SARS-CoV-2 remains an issue. Viral spread and increased infections has spurred non-pharmaceutical measures in children's environment, especially schools. Strategies to limit the spread of infection has included closure of most public spaces, including school buildings. Students have been required to learn from their homes, and many lost access to meals and other services provided at schools and structures vital to their physical, mental, social, and emotional well-being.

Considering the potentially detrimental effect of school building closures on students and families, school leaders across North Carolina sought partnerships with scientists, physicians, and public health specialists from Duke University and the University of North Carolina to better understand the science and data about COVID-19 and K-12 schools. Together, through the ABC Science Collaborative, school leaders and scientists monitored data from school districts choosing to gradually return to school buildings. Scientists interpreted the data and identified that contrary to existing assumptions, schools with mitigation strategies in place were not the

source of infection spread; in fact, data suggested that school buildings were likely safer than surrounding communities. ABC scientists published these results and discussed them with local, state, national, and international leaders. Ultimately, the results led to policy changes and guidance that changed the paradigm of children returning safely to school amidst a global pandemic. Perhaps most importantly, the collaboration between schools and scientists resulted in actionable, on-the-ground plans for safe school return that took into account the unique features and needs of each school district and local community.

Now that school buildings have reopened and K-12 students have returned, another crisis for children and families persists – COVID-19-related impacts on mental health. Health systems and schools have seen suicides skyrocket, schools are facing unprecedented classroom behavioral disruptions, and students with anxiety and depression have risen significantly. According to the Adolescent Behaviors and Experiences Survey (ABES) collected by the CDC in 2021, 37% of high school students reported experiencing poor mental health, and 44% indicated persistently feeling sad or hopeless during the pandemic. Schools and school systems are once again requesting support.

### **2.1.1 Background of Professional Development Workshop and Evaluation**

In addition to the direct pandemic-mediated impact on children, teachers' attitudes can impact their students' mental health. We also suspect school staff may play a role in students' mental health. Thus, Cultivating Awareness and Resilience in Education (CARE) has been proposed as a potential professional development workshop to help improve teachers' and staff's mental health, well-being, effectiveness and student wellness. CARE provides teachers and staff with tools and resources to reduce stress, prevent burnout, enliven teaching, and help students thrive socially, emotionally, and academically. The program will be presented in one to four face-to-face training sessions, spread out over one to four months, and provides post-training resources as additional support. CARE blends instruction with experiential activities, reflection, and discussion. Tools used by the program include mindful awareness practices, emotion, and caring skills training to support more equitable and caring classrooms. Research showed CARE workshops help improve emotional awareness, self-regulation, well-being, cardiovascular health, efficacies, mindfulness, and burnout/time-related stress. Improving teachers' ability to handle their own stress allows them to provide better emotional support to their students and may also help reduce schools' teacher attrition.

As part of this study, people who participate in CARE will be asked to answer questionnaires about demographic information, mental health, well-being, classroom instruction, and behavior management prior to the workshop and two times after completing the workshop. The ABC Science Collaborative is providing this professional development workshop as a service that participating schools offer to all teachers and staff. Those that want to participate in pre- and post-intervention assessments will be consented prior to doing so. Participation in the intervention and assessment completion is optional.

## **2.2 Scientific Rationale**

This study will examine the mental health and well-being of school teachers and staff after providing professional development to address teacher and staff self-efficacy, burnout, anxiety, depression, and stress. This behavioral intervention approach is necessary because the mental health of teachers, school staff, and children has declined since the beginning of the COVID-19 pandemic.

Teachers and staff can play a pivotal role in students' lives by developing supportive relationships and a classroom climate that promotes positive developmental outcomes and is

more conducive to learning. The ability of teachers and staff to play this role is compromised by the highly stressful emotional situations they encounter in the school environment that can lead to burnout. Teachers that exhibit burnout create learning environments that may cause harmful effects on students, especially those already at risk of mental health problems. This behavioral intervention may help teachers and staff apply concepts to reduce stress, and aid teachers improve classroom management and climate that could positively impact children's mental health. Specifically, a growing body of evidence has demonstrated a positive relationship between teacher well-being, school climate, and student outcomes, such as learning, growth, and mental health. Moreover, we can help promote student mental health and young people's ability to cope with daily stresses by supporting school personnel and promoting their self-efficacy to teach effectively, manage behavioral disruptions, avoid burnout, and reduce their levels of anxiety, depression, and stress. This intervention therefore adopts a "whole-school approach" to support teacher and staff and student wellness.

## **2.3 Potential Benefits**

Direct benefit may include reduced stress and improved performance in teachers and staff. The intervention may benefit the mental health and well-being of teachers and staff participating in the intervention, as well as the mental health of children.

## **2.4 Known Potential Risks**

This study is minimal risk, with the only identifiable risk being the potential loss of confidentiality.

### **Potential Risk of Loss of Confidentiality:**

Loss of confidentiality is a potential risk. There is a potential risk of loss of confidentiality with identifiable data collected directly from the participant. Every effort will be made to protect the participants' protected health information as well as other identifying information, but this cannot be guaranteed.

### 3 OBJECTIVES AND OUTCOME MEASURES

	Objective	Outcome Measures	Endpoints
Primary:	Evaluate the impact of a teacher resilience program on mental health and well-being outcomes of K-12 teachers and staff	CARE assessments, including Teachers' Sense of Efficacy Scale, Maslach Burnout Inventory, Symptoms of anxiety Generalized Anxiety Disorder 7 (GAD7), Symptoms of depression - Patient Health Questionnaire 8 (PHQ-8), Perceived Stress Scale (PSS)	Change in CARE assessments after the intervention compared to before
Exploratory:	Examine teacher and staff classroom instruction and behavior management	Experiences with the CARE for Teachers and Staff Professional Development Program 	Teacher and staff perceptions of changes in classroom instruction and behavior management after professional development (post-test only)

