### 4 STUDY DESIGN

#### 4.1 Overall Design

**Study design:** This is a prospective behavioral intervention. The intervention is a professional development program for K-12 teachers and staff. The primary objective is to evaluate the impact of a professional development intervention on school teacher and staff mental health and well-being outcomes, such as their self-efficacy and stress. Exploratory objectives include change in teacher and staff classroom instruction and behavior management after participating in the intervention. Individual participant-level data will be collected directly from teachers and staff who consent to participate in the intervention. A pre-intervention assessment and two post-intervention assessments will be collected. The consent will be administered once, electronically, via REDCap before collecting pre-intervention assessments. All assessments will be administered via REDCap.

**Study intervention:** A prospective behavioral intervention

**Duration of participant's enrollment:** Up to 1 year

**Duration of study:** Up to 2 years

**Safety:** N/A

 Based on the scale there is no pre-intervention validated measurement so only a post-intervention measurement is being used.

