## 9 STATISTICAL CONSIDERATIONS

### 9.1 Study Endpoints

#### 9.1.1 Primary Endpoints

Primary Objective: Examine the impact of a teacher resilience program on mental health and well-being outcomes of K-12 teachers and staff (administrative and non-administrative).

Primary Endpoint: Change in CARE assessment scores after the intervention compared to before.

- Teacher cohort 1: Change in raw CARE assessment scores (Teachers' Sense of Efficacy Scale; Maslach Burnout Inventory; Symptoms of anxiety Generalized Anxiety Disorder 7 (GAD7); Symptoms of depression - Patient Health Questionnaire 8 (PHQ-8); Perceived Stress Scale (PSS))
- Staff-non administrative cohort 2: Change in raw CARE assessment scores (Teachers' Sense of Efficacy Scale; Maslach Burnout Inventory; Symptoms of anxiety Generalized Anxiety Disorder 7 (GAD7); Symptoms of depression - Patient Health Questionnaire 8 (PHQ-8); Perceived Stress Scale (PSS))
- Staff administrative cohort 3: Change in raw CARE assessment scores (Teachers' Sense of Efficacy Scale; Maslach Burnout Inventory; Symptoms of anxiety Generalized Anxiety Disorder 7 (GAD7); Symptoms of depression - Patient Health Questionnaire 8 (PHQ-8); Perceived Stress Scale (PSS))

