### 9.2 Analysis Population

All participants enrolled to the study who completed the intervention will be included in the analysis population used for primary and exploratory objectives.

The number of participants who either completed the study or discontinued early from the study will be summarized using a CONSORT diagram. Demographic and characteristics at study baseline (1 week prior to intervention) will be summarized.

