### **9.3.1 Primary Analysis**

For the first primary endpoint for the teacher, staff administrative and staff non-administrative cohorts (change in CARE assessment scores after professional development intervention compared to before), the overall proportions will be reported and the change from pre- to post- will be presented in graphical form (bar chart).

95% confidence intervals for raw change in pre-post assessment scores for each assessment will be computed using a non-parametric bootstrap.

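### The primary objective is to evaluate the program's impact, but the planned analysis estimates only pre-post change among participants who completed it

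*Combined protocol and SAP*

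**What the plan says.** Section 3 gives the primary objective as "Evaluate the impact of a teacher resilience program on mental health and well-being outcomes of K-12 teachers and staff". The synopsis repeats it, Section 4.1 says "The primary objective is to evaluate the impact of a professional development intervention on school teacher and staff mental health and well-being outcomes", and Section 9.1.1 uses the same noun with 'examine' as the verb.

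The design behind that objective is as follows:

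- **Who receives the program.** The background section on the workshop describes the collaborative as "providing this professional development workshop as a service that participating schools offer to all teachers and staff". Taking part in the workshop and completing the assessments are both optional.
- **When outcomes are measured.** Section 4.1: "A pre-intervention assessment and two post-intervention assessments will be collected". Section 6.5.1 rules out any further assessments.
- **Who is analysed.** Section 9.2: "All participants enrolled to the study who completed the intervention will be included in the analysis population used for primary and exploratory objectives". Section 9.2.1 adds a per-protocol set that, for the primary endpoint, needs both a pre and a post assessment.
- **How it is analysed.** Section 9.3.1: "95% confidence intervals for raw change in pre-post assessment scores for each assessment will be computed using a non-parametric bootstrap", together with a bar chart of change.

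The teacher, administrative and non-administrative cohorts are strata by role. All three receive the program, so none serves as a comparator.

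**The concern.** 'Impact' asks what the program caused. The planned analysis answers a different question: how much did scores move among people who volunteered for the program, completed it and filled in the questionnaires?

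Movement over the interval can also come from the school calendar, from volunteers who enrol at a bad time and drift back towards their usual level, and from who stays to the end. Section 2.2 itself describes teacher and staff mental health as having worsened since the start of the pandemic, so the authors already treat these outcomes as moving over time.

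If the objective stands as worded, a confidence interval for raw change would be offered as the answer to it. A favourable trend could be reported as benefit, and an unfavourable one could hide a real benefit. Enrolling more people does not help, because the interval narrows around the sum of effect and trend. Section 14.7 foresees sharing results with school districts and in publications, where that distinction is easily lost.

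**Working it through.** **1. No figure to reproduce.** Section 9.4 states that no sample size calculation was made. The documents give no effect size, SD or correlation.

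**2. Objective against analysis.**

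| Element | Needed for 'impact' | In the plan |
|---|---|---|
| Comparator | Outcomes without the program over the same period | None described (4.1, 9.2, 9.3.1) |
| Pre-program trend | Two or more pre-assessments | One (4.1) |
| Population | Not selected by completion | Volunteers who completed (9.2) |
| Estimator | One that removes trend | Raw change (9.3.1) |

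The expected raw change among completers is program effect + time trend + regression to the mean, averaged over those who enrolled and stayed. Nothing in Section 9.3.1 removes the second or third term.

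**3. Length of the gap.** Inputs from Sections 4.2 and 6.1: pre-assessment sent up to 1 month before the workshop; workshop spread over up to 4 months; post-assessments sent at 1 week (7/30.4 = 0.23 month) and 2 months.

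- One-week follow-up: 1 + 4 + 0.23 = 5.23 months
- Two-month follow-up: 1 + 4 + 2 = 7 months

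These windows govern distribution. No closing date for completion is given, so the sums are the limits of the stated windows and not strict maxima.

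**4. Illustration of size.** All of these are assumptions: outcome SD 1; pre-post correlation r from 0.4 to 0.8; background drift d of 0.04 or 0.10 SD; n of 100 or 300; independent participants.

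- SD of change = √(2(1 − r)) = 1.095, 0.894, 0.632 at r = 0.4, 0.6, 0.8
- SE = SD of change / √n
- Chance that the 95% interval contains the program effect = Φ(1.96 − d/SE) − Φ(−1.96 − d/SE)

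| d | n | r = 0.4 | r = 0.6 | r = 0.8 |
|---|---|---|---|---|
| 0.10 | 100 | 0.850 | 0.799 | 0.647 |
| 0.10 | 300 | 0.647 | 0.509 | 0.218 |
| 0.04 | 100 | 0.935 | 0.927 | 0.903 |
| 0.04 | 300 | 0.903 | 0.879 | 0.805 |

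With d = 0 the figure is 0.95. A percentile-bootstrap simulation at r = 0.6 with a true effect of 0.2 SD (1,000 runs) gave 0.77 and 0.51 for d = 0.10, and 0.90 and 0.88 for d = 0.04, at n = 100 and 300.

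The mirror case has no program effect and d = 0.10. The chance that the interval excludes zero is Φ(d/SE − 1.96) + Φ(−d/SE − 1.96). For r from 0.5 to 0.7 that is 17% to 25% at n = 100 and 41% to 61% at n = 300.

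Clustering in workshops of 30 to 35 people would change the interval's width but not its shift by d.

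**5. Regression to the mean.** Expected change without any effect = (1 − r) × s, where s is how far volunteers start from their usual level. For an assumed s = 0.3 SD: 0.5 × 0.3 = 0.15 SD at r = 0.5, and 0.3 × 0.3 = 0.09 SD at r = 0.7.

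**The case against.** **The plan is already descriptive where it counts.** The endpoint is defined as change from before to after, Section 9.3.1 promises an interval for raw change, and there is no hypothesis test, success criterion or power claim. For raw change itself, the same model gives 95% coverage. This stands. It shows that the objective is the part out of line, and it is why the remedy is confined to wording. It does not remove the mismatch, because the objective appears as 'impact' in four places and no limitation on causal reading is stated.

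**Gap lengths vary, and Section 9.3 defers detailed methods to a later SAP.** A reader might infer that separating effect from trend is mathematically impossible here. The documents do not support that. The pre-assessment lead can vary up to a month and the workshop spread from one to four months, so a model with a common linear trend could be estimated. It would be weakly informed, would need the effect to be unrelated to gap length, and would leave regression to the mean and selection untouched. The supportable statement is that the planned raw change does not make the separation. A later SAP could add a time term or a caveat. It could not add an untreated group or a second pre-assessment to data already collected.

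**The coverage figures rest on invented inputs.** They do, and they are illustrations only. A reader might also carry them up to 1,000 participants. That is not supported: 1,000 is the cap on total enrolment, while the analysis is by cohort among completers.

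**The study-design schematic** listed in the contents was not in the text available here. A caveat there cannot be excluded. A comparator is unlikely, given Sections 4.1, 9.2 and 9.3.1.

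**Conclusion.** The point holds as a mismatch between the stated objective and what the planned analysis can show. The analysis estimates change among volunteers who completed the program. It does not separate a program effect from time trend, regression to the mean or selection, over a gap that the stated windows allow to reach roughly 5 or 7 months. This conclusion rests on the text alone and needs no assumed drift.

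The size of any error is unknown, and so is its direction. A reader might infer that a trend is shown to exist, or that the primary analysis is wrong and must be replaced. Neither follows. The documents give no trend over the study interval, and the raw change with its interval is a reasonable summary for a descriptive objective. The data stay usable. The wording should be changed before results are reported, because it governs what may be concluded from them.

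**What to change.** In the synopsis and Sections 3, 4.1 and 9.1.1, replace the 'impact' objective with:

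> Describe the change in mental health and well-being among K-12 teachers and staff from before to after a teacher resilience program.

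Add to Section 9.3.1:

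> Change is reported by cohort among participants who completed the program and is not attributed to the program, because there is no concurrent comparator and time trends, regression to the mean and self-selection cannot be separated from a program effect.

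The endpoint, data collection and primary analysis stay as planned. The cost is a few sentences and a more modest claim.

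A separate matter, which adds no weight to this point: Section 9.2 places baseline one week before the intervention, while Sections 4.2, 6.1, 6.2, 6.5.1 and 13.1 allow up to one month. These should be reconciled.

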### 4 STUDY DESIGN

#### 4.1 Overall Design

**Study design:** This is a prospective behavioral intervention. The intervention is a professional development program for K-12 teachers and staff. The primary objective is to evaluate the impact of a professional development intervention on school teacher and staff mental health and well-being outcomes, such as their self-efficacy and stress. Exploratory objectives include change in teacher and staff classroom instruction and behavior management after participating in the intervention. Individual participant-level data will be collected directly from teachers and staff who consent to participate in the intervention. A pre-intervention assessment and two post-intervention assessments will be collected. The consent will be administered once, electronically, via REDCap before collecting pre-intervention assessments. All assessments will be administered via REDCap.

**Study intervention:** A prospective behavioral intervention

**Duration of participant's enrollment:** Up to 1 year

**Duration of study:** Up to 2 years

**Safety:** N/A

 Based on the scale there is no pre-intervention validated measurement so only a post-intervention measurement is being used.

